6.2.5 Identification, traceability and labelling of the *In vitro* Diagnostic Test

Table: DOAC urine test strip

Name:	DOAC Dipstick
Manufacturer:	DOASENSE GmbH, Heidelberg
Model/Type:	DOASENSE REF Number: 0001

Confidentiality Statement

This document is confidential and proprietary to Sponsor and HLZ Medizinische Statistik and for restricted circulation and access only. No part of it may be transmitted, reproduced, published or used by any person/s without prior written authorization.

Lot number:	DS 18021901
Expiration date:	2019 05 as of December 2018
Intended use:	Analysis of the presence or absence of DOACs in urine and of normal or low concentration of creatinine
Contraindications:	known intolerance to DOACs
CE certification:	CE marked DIMDI registration number: DE/CA 38/00141004
Packaging:	Container (12 test strips) including reference color chart

CE: Certification (Conformité Européene [European Conformity])

DOAC: Direct oral anticoagulant

The packaging and the instructions for use will indicate that the device is only intended for the Post Marketing Study according to this Study Plan.

The sponsor will supply the investigators and clinical investigation sites with the test, including all relevant documentation.

Used test strips will be discarded into the standard containers of the site for collection of tubes containing blood or urine samples. Unused test strips will be returned to the sponsor.

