8. DEFINITIONS AND DERIVED VARIABLES

All measurements are carried out according to standard medical methods of the investigational site. The personnel involved are adequately trained in required measurements.

Patients will collect a sample of urine into the container provided by DOASENSE GmbH and hand it over to the site personnel.

The site personnel will first perform

- 1) Visual testing using DOAC Dipstick according to the instructions for use (annex 2)

Confidentiality Statement

This document is confidential and proprietary to Sponsor and HLZ Medizinische Statistik and for restricted circulation and access only. No part of it may be transmitted, reproduced, published or used by any person/s without prior written authorization.

Sponsor Name: DOASENSE GmbH
Statistical Analysis Plan (SAP)
Version No.: 3 Date: 2019-05-15

Sponsor Study No.: DOA-CS-002
ClinicalTrials.gov ID: NCT03182829
HLZ Medizinische Statistik Study No.: 1-2019

- 2) immediately thereafter analyze the patient's DOAC Dipstick with the DOASENSE Reader (annex 3). The printout of the DOASENSE Reader is attached to the respective field in the CRF with the numbers to be written with a pencil beside the printout because the thermopaper of the printout may lose colour over time.
- 3) put two aliquots of 5 mL urine into the tubes provided for measurements of DOACs and creatinine.
- 4) to discard the remaining urine.
- 5) Analysis of DOASENSE Control Urines that comprise a negative and positive control for DOACs and creatinine before and after inclusion of every 12th patient
- 6) Compilation of a questionnaire on the handling of DOAC Dipstick and its analysis by the study personnel that perform the test (visual and with DOASENSE Reader) after having performed the analyses of the 5th and 15th patient

All sites will receive the same model/type of reflectance photometric dipstick color reader (DOASENSE Reader).

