8.3 Assessment of DOAC Dipstick by DOASENSE Reader

Measurement

After the urine strip has been immersed in the urine sample for approx. 2-3 seconds according to the instructions for use, the strip is placed on the strip holder of the DOASENSE Reader after 10 minutes and the START button is pressed. The device pulls the strip holder and carries out the measurement. The result of the four pads is displayed on the screen and printed on the thermal printer. After measuring the strip, the device ejects the strip holder. The strip is removed and disposed of.

The output of DOASENSE Reader are 3-digit values reprinting the %REM values (reflectance units) of the 4 pads and printed by the Reader of the printer for each measurement that is attached with an adhesive by the study personal into the CRF. These values are then written with a ball point pen on the right part of the printed values because the printout may lose color over time.

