8.6 Assessment of DOASENSE Control Urines

At start of study, and after every 12th examination of patient urine samples, on a DOAC Dipsticks are analysed by the visual reading and by DOASENSE Reader using DOASENSE Control Urines that are a negative control (0 ng/mL Rivaroxaban and Dabigatran, 1.5 g/L

Confidentiality Statement

This document is confidential and proprietary to Sponsor and HLZ Medizinische Statistik and for restricted circulation and access only. No part of it may be transmitted, reproduced, published or used by any person/s without prior written authorization.

creatinine and normal urine colour) and a positive control (800 ng/mL Rivaroxaban and Dabigatran and no creatinine) as described above. The results are documented on a separate page of the CRF (Quality Control to be performed at start of Study, and after every 12th Examination of Patient Urine Samples (9.5.3. Page 21, Study Protocol)) (annex5) provided by DOASENSE.

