This document is confidential and proprietary to Sponsor and HLZ Medizinische Statistik and for restricted circulation and access only. No part of it may be transmitted, reproduced, published or used by any person/s without prior written authorization.

Creatinine

XI. Comparison of **quantitative creatinine** of Limbach (Jaffe Method) with **qualitative results of DOASENSE Reader**. A cut-off value of creatinine (g/L) needs to be determined for the colours low to normal by DOASENSE Reader. Differences between Readers needs to be analyzed.
Statistical methods: determination of a cut-off value, McNemar test, kappa index, accuracy, sensitivity, specificity, positive and negative predictive values.

XII. Comparison of results of **qualitative of creatinine by DOAC Dipstick** with **qualitative results of DOASENSE Reader**. Analysis of normal ranges of the **quantitative** results of **Urine Colour Pad of DOASENSE Reader**.
Statistical methods: McNemar test, kappa index, accuracy, sensitivity, specificity, positive and negative predictive values.

Urine Colour

XIII. Analysis of normal ranges of the **quantitative** results of **Urine Colour Pad of DOASENSE Reader**.
Statistical method: Descriptive statistic

XIV. Analysis of an interaction of the **qualitative results** of the pad **Urine Colour** on the results of the qualitative results of the pads of Factor Xa inhibitor, thrombin inhibitor and creatinine of **DOAC Dipstick** with the qualitative results **DOASENSE Reader**.

Other

Statistical method: multivariable regression analysis using SELECTION=FORWARD method

XV. Analysis of the results of **DOASENSE control urines** over time and influence on results of DOAC Dipstick and DOASENSE Reader.
Statistical method: McNemar test, kappa index, accuracy, sensitivity, specificity, positive and negative predictive values.

Confidentiality Statement

This document is confidential and proprietary to Sponsor and HLZ Medizinische Statistik and for restricted circulation and access only. No part of it may be transmitted, reproduced, published or used by any person/s without prior written authorization.

XVI. Descriptive analysis of **Drop-out** patients (case reports)
Statistical method: Descriptive statistic

XVII. Analysis of the results of the **questionnaire** and interaction on results of **DOAC Dipstick**. Center effects need to be analysed.
Statistical method: multivariable regression analysis using SELECTION=FORWARD method.

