23. Analysis of changes results of DOASENSE Control Urines over time and influence on results of pads of DOAC Dipstick over time
24. Descriptive results of Questionnaire over time and differences between centres
25. Interaction of results of questionnaire with results of DOAC Dipstick

19. LIST OF POST-TEXT-TABLES AND FIGURES**Figures**

1. Results of all data of tables no 3 to 21 whenever possible as column diagrams with respective text (header)
2. ROC Curves when applicable with respective text (Header)

Confidentiality Statement

This document is confidential and proprietary to Sponsor and HLZ Medizinische Statistik and for restricted circulation and access only. No part of it may be transmitted, reproduced, published or used by any person/s without prior written authorization.

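### The methods named for the control-urine endpoint contain no time term and no link to patients, so as specified they cannot test or quantify drift

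*SAP*

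**What the plan says.** The endpoint is item XV in section 10.2.2 (numbered XVI in section 9.2.4). It covers the results of the control urines "over time and influence on results of DOAC Dipstick and DOASENSE Reader". The method line reads "Statistical method: McNemar test, kappa index, accuracy, sensitivity, specificity, positive and negative predictive values", and nothing more is specified there.

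The data behind it are described as follows.

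- **Timing.** Section 8.6 has the controls run "At start of study, and after every 12th examination of patient urine samples". Section 8 words the schedule differently: "Analysis of DOASENSE Control Urines that comprise a negative and positive control for DOACs and creatinine before and after inclusion of every 12th patient".
- **Content.** The content is fixed and known. The positive control, for example, is "800 ng/mL Rivaroxaban and Dabigatran and no creatinine" (section 8.6).
- **Reader output.** Section 8.3 states "The output of DOASENSE Reader are 3-digit values reprinting the %REM values (reflectance units) of the 4 pads". Each centre has its own Reader (item III).
- **Strips.** Section 6.2.5 lists one lot, with expiry given as "2019 05 as of December 2018".

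Related output is listed elsewhere.

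- Table 23 in section 18 is "Analysis of changes results of DOASENSE Control Urines over time and influence on results of pads of DOAC Dipstick over time".
- Table 22 covers control-urine results and differences between centres.
- In the label table of section 10.1.5, row 8 lists control urines with qualitative and quantitative Reader results, for description and analysis of influence. Row 10 lists time dependence of the Dipstick parameters, labelled as descriptive.

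None of these entries names an inferential method for time.

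**The concern.** Item XV asks two questions: do control results change during the study, and do such changes carry over to patient results? The listed methods answer a third question, namely how often two classifications agree overall. The same list serves the method-comparison items (item XII, for instance), where it fits. For its other interaction or influence questions (items VII to X, XIV and XVII) the SAP assigns multivariable regression.

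What is at stake is the check on the stability of the measuring system. The objective in section 6.2 (sample size) is to show false-negative and false-positive proportions below 5%, pooled over the study. If strips or a Reader changed during recruitment, a pooled rate would average good and poor periods. The control urines are the built-in means of finding that out. If item XV is carried out as written, a late run of failures and the same number of random failures would be reported identically.

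**Working it through.** The SAP gives no figure for this item, so there is none to reproduce. The check is of the property that matters: do the listed statistics respond to time order?

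**1. Question against method.** Change over time needs a time variable or a stated pairing of early with late runs; item XV gives neither. Influence on patient results needs a rule linking controls to patients; none is given. Sensitivity, kappa and McNemar need two-category results, so a reflectance shift that does not cross the cut-off leaves them all unchanged.

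**2. Number of control rounds.** 440 patients per group × 2 groups = 880 (section 6.2). 880 / 12 = 73.3, so about 73 rounds, before adding the start run at each centre. The number of centres is not given.

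**3. Order check (illustrative).** Take 73 positive and 73 negative control runs, with five positive-control failures (an assumed number). Case A: the last five positive runs fail. Case B: failures at runs 4, 19, 35, 51 and 67.

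| Statistic | Calculation | A (late) | B (scattered) |
|---|---|---|---|
| Sensitivity | 68/73 | 0.932 | 0.932 |
| Specificity | 73/73 | 1.000 | 1.000 |
| Accuracy | 141/146 | 0.966 | 0.966 |
| Kappa against known status | (0.966 − 0.5)/(1 − 0.5) | 0.93 | 0.93 |
| Exact McNemar against known status | 2 × 0.5⁵ | 0.0625 | 0.0625 |
| Rank-sum of failure against run order | see below | 0.0002 | 0.85 |

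If the visual reading and the Reader fail on the same runs, their kappa is 1.00 and McNemar p = 1.00 in both cases.

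The rank-sum statistic has mean 5 × 68/2 = 170 and variance 5 × 68 × 74/12 = 2096.7 (SD 45.8). Late failures give U = 340, z = (170 − 0.5)/45.8 = 3.70. Scattered failures give U = 161, z = (9 − 0.5)/45.8 = 0.19. Only the statistic that uses order separates the cases.

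**4. What a slope could show.** Let n control readings be spread evenly over a study period scaled to 0–1, with within-control SD σ and total drift δσ. Then SE(drift) = σ/√(n/12), and power at two-sided α = 0.01 (section 10.1.5) is about Φ(δ√(n/12) − 2.576). With n = 73, √(73/12) = 2.466.

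- δ = 1: Φ(2.466 − 2.576) = 0.46 (simulated 0.455).
- δ = 1.5: Φ(3.700 − 2.576) = 0.87 (simulated 0.855).

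The drift sizes are assumptions, and the calculation treats all rounds as one series with a drift common to every Reader.

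**5. One Reader alone.** A centre with 30 patients has about three rounds on the section 8.6 schedule (start, after 12, after 24). At times 0, 0.5 and 1 the sum of squares is 0.5, so SE(drift) = σ/√0.5 = 1.41σ. A drift of 1.5σ is then 1.5/1.41 = 1.06 standard errors.

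**The case against.** Four arguments can be made on the other side.

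*The SAP plans time-related output elsewhere.* This is true. A reader might infer from item XV that drift cannot be detected at all in this study, or that reflectance values on controls go unused. The documents do not support either. Rows 8 and 10 of the label table and Tables 22 and 23 plan time-related, between-centre and quantitative Reader output, so a change could be seen descriptively. What remains is that row 10 is explicitly descriptive and Table 23 has no method attached.

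*McNemar is a paired test.* If the start run were paired with a later run, or the runs before and after each block of 12, it would test change. Saying that the listed methods have no power whatever would therefore go too far. But the SAP states no such pairing, and pairing would still leave the reflectance values and the link to patients untouched.

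*Drift is speculative.* It is. Section 6.2.5 gives an expiry of May 2019 and this SAP version is dated 15 May 2019, from which a reader might infer that strips were used at or past expiry. The SAP gives no testing dates, and nothing in it shows fading or Reader instability. The point is that the check should work, not that drift occurred.

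*The plan allows changes.* Section 10.1.5 lets unsuitable methods be replaced, with documentation in the report, and section 10.2.2 allows additional evaluations. This limits the harm, but it leaves the choice of method until the data are seen.

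**Conclusion.** The point holds in this form: the methods named for item XV include no time variable, use only qualitative results and do not link controls to patients. As specified they cannot test or quantify drift in the control urines, or its influence on patient results. Drift could still be noticed in the descriptive output listed in sections 10.1.5 and 18.

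That the listed statistics ignore run order follows from their definition once runs are pooled; it does not depend on the illustrative failure count. It does rest on reading item XV as having no early-versus-late pairing, since none is written. The power figures (about 46% for a drift of 1 SD and 86% for 1.5 SD over 73 rounds) are illustrative. They assume a drift shared by all Readers and do not apply to a single drifting Reader.

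This is a secondary quality-control item and does not alter the primary analysis. It should be corrected because following the stated method would not answer the item's own question.

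**What to change.** Amend item XV and name the same method for Table 23.

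1. **Change over time.** For each pad and control level, regress control %REM on run date, or on run number within centre if the date is not recorded, with a Reader/centre effect. For visual pass/fail, use logistic regression on run order. Report each slope with its confidence interval.
2. **Influence on patients.** Attach to each patient the nearest preceding control result at the same centre and relate it to false-negative and false-positive status against LC-MS/MS.
3. **Description.** Keep accuracy, sensitivity, specificity, predictive values and kappa on controls as summaries.
4. **Schedule.** Align the control timing in sections 8 and 8.6, since it determines the number of runs and which control precedes which patient.

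The cost is SAP wording and a small number of additional models. Whether every control run carries a date depends on the quality-control form (annex 5), which is not shown; run number is the fallback.

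The main limitation is precision. Small centres contribute only a few rounds, so Reader-specific slopes will be wide and should be reported as such. Step 2 is limited too: at the SAP's assumed 2.5% error rate, applied for illustration to all 440 × 0.88 = 387 evaluable patients in a group, there would be about 387 × 0.025 ≈ 10 errors, enough for an estimate with a wide interval and little more.

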6.3 Study Time points

During a routine visit in the outpatient care unit of the site, patients who match the entry criteria (based on their medical records at the site) will be informed about the Post Marketing Study, and informed consent will be obtained.

Upon patient's written informed consent the investigator will document the patient's demographic characteristics and record the time of last intake of DOAC in the CRF. Then, the patients will provide a sample of urine and give it to the respective site personnel. The patient requires no further action.

The site personnel will put two aliquots of urine (5 mL) into provided test tubes for analysis of the concentration of DOACs and prepare the sample for shipment according to the shipment instructions.

Then, the site personnel will perform the visual and reflectance photometric reading of the DOAC Dipstick.

Thereafter, the site personnel will complete the questionnaire.

Confidentiality Statement

This document is confidential and proprietary to Sponsor and HLZ Medizinische Statistik and for restricted circulation and access only. No part of it may be transmitted, reproduced, published or used by any person/s without prior written authorization.

Assessment	Day 1
Informed consent	X
Demographic data, medical history	X
Medication history (DOACs, other)	X
Collection of urine sample	X
Visual reading presence/absence of DOACs (IVD)	X
Reflectance photometric reading (DOASENSE Reader) of DOAC Dipstick	X
Urine aliquot for bioanalysis (LC_MS/MS)	X
Completion of questionnaire	X

DOACs: direct oral anticoagulants, IVD: *in vitro* diagnostic test

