8.7 Questionnaire on user handling of DOAC Dipstick

The aim of the content of the questionnaire is to gather information on the handling and the performance of DOAC Dipstick by the user. A questionnaire that contains statements on the handling of DOAC Dipstick and the colour scale has to be compiled by the study personnel who perform the testing with DOAC Dipstick after the analysis of the 5th and 15th patient (annex 6).

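### Item XVII relates site-level questionnaire answers to per-patient strip results by forward selection, with no clustering by centre and no rule that centre stays in the model

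*SAP*

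**What the plan says.** - **Timing.** Section 8, step 6, has the staff who perform the test complete the questionnaire "after having performed the analyses of the 5th and 15th patient". Section 8.7 gives the same two time points. Section 6.3 differs: it describes a single patient's visit and ends with "Thereafter, the site personnel will complete the questionnaire", and its Day 1 table lists the questionnaire.
- **Analysis.** Section 10.2.2, item XVII (numbered XVIII in section 9.2.4), plans "Analysis of the results of the questionnaire and interaction on results of DOAC Dipstick". The method is "Statistical method: multivariable regression analysis using SELECTION=FORWARD method". On centre it says only "Center effects need to be analysed".
- **Output.** Row 13 of the label table in section 10.1.5 and Table 25 in section 18 ("Interaction of results of questionnaire with results of DOAC Dipstick") carry this analysis. Row 12 and Table 24 give the questionnaire descriptively.
- **Not stated.** Item XVII gives no unit of analysis, no rule linking a questionnaire to patients, no random effect or clustered variance, no entry level and no candidate list. Nothing requires centre to stay in the model, and section 10.1.9 does not stratify by centre in general.

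**The concern.** The explanatory variable describes a site's users at two moments; the outcome is measured once per patient. A regression on patient rows repeats one answer over many patients and counts each repetition as new information, unless the model accounts for centre. Item XVII mentions centre effects but leaves it to data-driven selection whether centre enters. So the planned text can yield either p-values that ignore clustering or an estimate resting on a weak before-and-after contrast, and nobody can tell in advance which. At stake is whether a reported link between handling answers and strip results can be believed.

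**Working it through.** **Inputs from the SAP.** Section 6.2 (sample size): 440 per group including 12% dropout, so 2 × 440 = 880 enrolled and 880 × 0.88 ≈ 774 evaluable; assumed error rate 2.5%. Section 10.1.5: two-sided α = 0.01. The SAP states no figure for item XVII, so there is none to reproduce.

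**Assumptions (not in the SAP).** 18 to 40 sites, the ICCs shown, a correlation r of 0.5 to 0.8 between a site's two answers, and 10 questionnaire items. One respondent per site is assumed.

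**Step 1: information available.** Two questionnaires per site give 2 × 18 = 36 to 2 × 40 = 80 distinct records for 880 patients.

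**Step 2: centre not in the model.** For one site-level score and m patients per site, the variance is understated by DE = 1 + (m − 1) × ICC. A nominal 0.01 test then rejects with probability of about 2Φ(−2.576/√DE). The between-centre SD at a 2.5% mean is √(ICC × 0.025 × 0.975). The simulations used beta-binomial errors and no true effect.

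| ICC (probability scale) | Between-centre SD | 18 × 43: DE, formula | 18 × 43: simulated | 26 × 30: DE, formula | 26 × 30: simulated |
|---|---|---|---|---|---|
| 0.01 | 1.6 points | 1.42, 3.1% | 2.7-3.2% | 1.29, 2.3% | 1.3-2.1% |
| 0.02 | 2.2 points | 1.84, 5.8% | 4.3-4.5% | 1.58, 4.0% | 2.9-3.1% |
| 0.05 | 3.5 points | 3.10, 14.4% | 11.0-12.5% | 2.45, 10.0% | 7.5-8.2% |

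At ICC 0 the simulated rate was 0.7-0.8%. The formula is a large-sample guide; with few centres and a rare outcome the simulated values are the better ones. In a second simulation with two scores per site (patients 1-14 and 15 onward), 880 patients and a logit-scale ICC of 0.05, the rate was 1-3%. That ICC is only about 0.0045 on the probability scale, so the two sets of results do not conflict.

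**Step 3: centre in as a fixed effect.** If the first score covers patients 1-14 and the second the rest, the within-site share of an item's variance is w(1 − w) × 2(1 − r), with w = 14/m.
- m = 49 (18 sites): 0.286 × 0.714 × 1.0 = 0.204 at r = 0.5; × 0.4 = 0.082 at r = 0.8.
- m = 22 (40 sites): 0.636 × 0.364 × 1.0 = 0.231 at r = 0.5; × 0.4 = 0.093 at r = 0.8.

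Centre therefore explains about 77-80% or 91-92% of the item. Simulation with finite numbers of sites gave 74-78% and 89-91%, with a variance inflation of about 4 to 13. A site that never reaches its 15th patient contributes nothing. What remains compares early with later patients, so it is confounded with time and learning. The test for one pre-named item is near nominal here (0.0-2.5% in 200 runs): the fault is imprecision, not a false p-value.

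**Step 4: forward selection.** For 10 independent null items at an assumed entry level of 0.01, the chance that at least one enters is 1 − 0.99^10 = 9.6%. Simulation gave 8-10% without clustering, and 13-16% at logit-scale ICC 0.05 with a 2.5% outcome. With centre forced in, at least one of the 10 was significant in about 7-14% of runs. With centre as a mere candidate and ICC 0.05-0.1, a null item entered in 9-22% of runs (2.5% and 50% outcomes together); at the 2.5% outcome centre itself entered in only 5-18%.

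**The case against.** The strongest reply is that item XVII does recognise centre and that section 10.1.5 lets unsuitable methods be replaced, with documentation. Neither settles the matter. Asking for centre effects does not keep centre in a forward-selected model, and a later change of method is made after the data are seen.

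Other objections stand and limit the point:

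- A reader might infer that the questionnaire is inseparable from centre and that its p-values are too small at the same time. These belong to different models: with centre in, the clustering inflation largely goes away; it arises when centre is left out.
- The table in Step 2 is not the planned analysis. It has one score per site, no centre term and no selection, and it takes strip error as the outcome, whereas item XVII says only results. ICC 0.05 at a 2.5% mean implies a between-centre SD larger than the mean itself.
- Two completions per site is the reading of sections 8 and 8.7. Section 6.3 can be read as every visit, and several staff may respond. The answers would still come from site staff and cluster by site.
- A reader might infer that the usability objective is lost. It is not: row 12 and Table 24 still serve it descriptively.

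**Conclusion.** The point holds as a defect in one late secondary analysis. The named method ignores clustering and does not secure centre in the model, and its selection step is anti-conservative even with no clustering. For one null item at nominal 0.01 and a 2.5% outcome, the false-positive rate is about 1-3% at small within-centre correlation and about 8-12% only at probability-scale ICC 0.05, which should be read as an extreme case. Selection over an assumed 10 items brings about 8-10% even at ICC 0. All these figures rest on assumed numbers of centres, ICCs and items, and on patient rows as the unit, which is inferred because strip results exist only per patient.

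The documents do not support saying that the model will produce false associations, only that it can. Row 13 and Table 25 are affected; the primary endpoint is not.

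**What to change.** 1. In item XVII, replace SELECTION=FORWARD with one pre-named questionnaire score, or a short pre-named list of items, analysed at site or site-period level. The site-period form keeps the change from the 5th to the 15th patient, which a single score per centre would discard.
2. If a patient-level model is wanted, use a random centre intercept or cluster-robust variance, and only if events allow. With strip error as outcome, 774 × 0.025 ≈ 19 errors are too few for a rich logistic mixed model.
3. State the Dipstick outcome, the rule linking each questionnaire to patients, and the number of centres as the effective sample size. Label the analysis exploratory.
4. Reconcile section 6.3 with sections 8 and 8.7 on when the questionnaire is completed.

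The simpler alternative is to report the questionnaire descriptively only and drop row 13 and Table 25.

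The cost is SAP wording. The stated precision will be lower, and there may be no formal test.
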